Protocol Non-CTIMP
Template Version 2.0 Review Date: December 2021

A cross-sectional study and a novel screening survey for radial artery assessment in surgical coronary revascularisation.

PROTOCOL

DATE 09/04/2024

CHIEF INVESTIGATOR – [name]

List Investigators – [name]
[name]
[name]

Investigation Sites: Royal Papworth Hospital; Royal Brompton Hospital

Principal Investigator: [name]

Protocol Identification Number: P00258

Date of Protocol: 20th November 2023

Review Date: 9th April 2024

Protocol Version Number: 4.0

Trial Sponsor: Royal Papworth Hospital (R&D Study Registration Number: P03105)

Contents

TRIAL OVERVIEW

1. Trial Overview	3
Primary Research Question	
Study Design	
Primary Outcome	
Secondary Outcome	
Rationale	
Schedule of Events	
2. Patient Recruitment	5
Study Population	
Inclusion Criteria	
Exclusion Criteria	
Recruitment Strategy	
3. Data Analysis and Document Retention	5
Sample Size	
Statistical Analysis	
4. Consent Process and Visit Schedule	6
Visit 1	
Follow-up Visit	
Informed Consent Procedure	
Table 1: Visit Schedule	
Table 2: Trial Specific Procedures versus Routine Procedures	
5. Follow up Visits and Travel Expenses	8
6. Data Collection and Auditing	9
Data Collection Form Completion	
Source Documentation	
Errors and Correcting	
Storage of Documents	
Retention of Documents	
Monitoring and Auditing	
7. Adverse and Serious Adverse Events	10
Recording & Reporting	
8. Amendments	11
Amendment log	

TRIAL OVERVIEW

1. Trial Overview

Primary Research Question

What factors influence the diagnostic accuracy of radial artery assessment in patients undergoing surgical coronary revascularisation?

Study Design

A multi-centre cross-sectional study to investigate the validity of radial artery assessment techniques in adults' people with ischaemic heart disease undergoing surgical coronary revascularisation with their radial artery being selected as an autologous graft conduit. Maximum expected duration of subject participation is 12 weeks.

Primary Outcome

Measure the sensitivity, specificity, negative and positive predictive values of the Modified Allen test (+/- pulse-oximetry), the Barbeau Test and ultrasonography examination.

Secondary Outcome(s)

- Measure the morphological and physiological quality of radial arteries through a validated structured questionnaire (Radial Artery Quality Evaluation Survey).

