- Measure the patients' finger movements, cold tolerance sensitivity and tactile/touch perception through an ordinal symptoms scale (Follow-up Radial Artery Harvesting Scale).

Rationale

The study will explore the accuracy of radial artery (RA) assessment in people with ischaemic heart disease (IHD) undergoing coronary artery bypass grafting (CABG). IHD affects 2.3 million people in the United Kingdom and is responsible for over 65,000 deaths per year. CABG results in the most effective therapeutic strategy for multi-vessel IHD while the RA is one of the preferred graft conduits. A comprehensive peri-operative RA assessment is essential to ensure disease-free RA segments are selected, precluding surgical complications such as hand ischaemia and graft failure. Whilst numerous screening tests are documented, their validity (diagnostic accuracy) is under debate. The literature is lacking evidence regarding the use of a standardised protocol for RA screening. The patients' experiences are seldom considered while surgical complications still occur. The expert opinion of professionals involved within the RA assessment and harvesting, generally the surgical care practitioners (SCP), is also not explored.

The intended research will provide an in-depth understanding of how assessment techniques inform RA harvesting in patients undergoing CABG, calibrating clinical decision and improving surgical practice. The research will uplift the SCP profession and address knowledge gaps, resulting in disciplinary and academic contributions.

Schedule of Events

Patients taking part in the study will receive an assessment of the arterial forearm circulation from their non-dominant upper extremity through the observations below.

- **Pre-operative observations.** Before surgery (in the ward environment after the patient is being admitted or whilst patient in the anaesthetic room) the forearm blood circulation is measured through the measures 1, 2, 3 and 4 to inform decision to surgically expose the RA.

1) Modified Allen Test (MAT). Instruct the patient to clench his/her wrist while the examiner occlude with three fingers the patient's ulnar and radial arteries; instruct the patient to unclench his/her wrist; release the ulnar artery. The MAT result is negative or positive considering in how long the palm flushes:

≤5 seconds negative MAT; good collateral hand circulation (suggesting harvestable radial artery)

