>5 seconds positive MAT; poor collateral hand circulation (suggesting not-harvestable radial artery)

2) Pulse-oximetry guided MAT. A pulse-oximetry probe is positioned on the patient's index finger; both radial and ulnar arteries are occluded by the examiner (with three fingers) until flattening of pulse waveform is obtained. Pressure on the ulnar artery is released and the result of the assessment is calculated considering in how long the pulse waveform returns to baseline:

≤5 seconds negative result (suggesting harvestable radial artery)
>5 seconds positive result (suggesting not harvestable radial artery)

3) Barbeau Test. A pulse-oximetry probe is positioned on the thumb; the radial artery is then compressed by the examiner, and the pulse waveform is analysed for up to 120 seconds, providing four patterns of ulnar-palmar patency:

- a. No damping of the pulse tracing immediately after compression (suggesting harvestable radial artery)
- b. Damping of the pulse tracing (suggesting harvestable radial artery)
- c. Loss of the pulse tracing, followed by recovery within 120 sec (suggesting harvestable radial artery)
- d. Loss of the pulse tracing, without recovery within 120 sec (suggesting not harvestable radial artery).

4) Ultrasonography examination of the forearm arteries. The radial artery is surgically exposed (negative result) when the following apply:

- a. ulnar artery inner diameter ≥2 mm
- b. radial artery inner diameter ≥2 mm
- c. absence of radial artery intraluminal calcifications and plaques.

- **Intra-operative observations.** The radial artery is surgically harvested when the following apply:

A) The radial artery morphological and physiological characteristics (diameter, calcifications, presence of pulsatile flow), quality of harvesting technique and surgical accessibility are considered satisfactory, good or optimal. Measures are taken through a structured questionnaire (Radial Artery Quality Evaluation Survey) currently being validated through a Delphi study.

B) Oxygen saturation reading (SpO_2) from the thumb through pulse-oximetry remains at 95% or above when an occlusive atraumatic clamp is applied on the mobilised RA.

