- *Recruitment review dates: June 2024, August 2024, November 2024, February 2024.*

Section 3. Sample Size and Data analysis

Sample Size

- A consecutive sampling method will be adopted for the recruitment of study participants. The minimum required number of participants to test and verify research hypotheses is sixty-nine patients (N=69). An adaptive trial design will be implemented: at quarterly assessment points the statistical power is assessed and the remaining sample size required is updated accordingly.

Statistical Analysis

- Sample size calculation was undertaken using G*Power software (version 3.1) using Chi-squared Test (χ^2) and adopting optimal effect size ($\omega=0.4$) and power (0.8).

4. Consent Process and Visit Schedule

Visit 1

- Potential participants will firstly be approached by clinicians within the healthcare team who is directly involved in delivering care and treatment to the patients. Clinicians will refer potential participants to the main investigator who will approach them for consenting purposes to take part in this study.

Follow-Up Visits

- Each patient will be assigned a study number; the study numbers will be allocated sequentially starting at 001.
- Visits should be scheduled and performed according to table 1.
- Trial specific procedures *versus* routine procedures are detailed in table 2 *if appropriate to the study*. The trial specific procedures will be performed after written informed consent has been obtained. The procedures that can be performed prior to consent being obtained are detailed in table 3 (*if appropriate*).

Table 1 Visit Schedule

Visit Number	Visit n	Visit n+1	Visit n+2
Time interval of Visit	week 0-3	week 0-3	week 4-12
Consent	X		
Pre-operative observation (Modified Allen Test +/- pulse-oximetry)		X	
Pre-operative observation (Barbeau Test)		X	
Pre-operative observation (Ultrasonography examination of forearm arteries)		X	
Intra-operative observation (oxygen saturation reading)		X	
Use of Questionnaire (Radial Artery Quality Evaluation Survey)		X	
Post-operative observation (Follow-up Radial Artery Harvesting Scale)			X

Table 2 Trial Specific Procedures *versus* Routine Procedures

Routine Investigations	Study Specific Procedures
Modified Allen Test +/- pulse-oximetry	Seeking Consent
Barbeau Test	Use of Questionnaire (Radial Artery Quality Evaluation Survey) currently under validation
Ultrasonography examination of forearm arteries	Use of Follow-up Radial Artery Harvesting Scale

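### The primary accuracy measures have no named reference standard, and verification of test-positive arteries is not secured, so ultrasound sensitivity, specificity and PPV may not be estimable

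*Combined protocol and SAP*

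**What the plan says.** - **Primary Outcome (section 1).** "Measure the sensitivity, specificity, negative and positive predictive values of the Modified Allen test (+/- pulse-oximetry), the Barbeau Test and ultrasonography examination". No comparator, target condition or reference standard is attached to these measures, here or elsewhere.
- **Direction of the tests (section 1, Schedule of Events).** For the oximetry-guided Allen test the wording is "negative result (suggesting harvestable radial artery", and the other tests run the same way. NPV is therefore the probability that an artery is harvestable given a negative test.
- **Pre-operative observations.** The forearm circulation is "measured through the measures 1, 2, 3 and 4 to inform decision to surgically expose the RA". For ultrasound the rule is explicit: "The radial artery is surgically exposed (negative result) when the following apply", followed by the diameter and calcification criteria. No pathway is described for an ultrasound-positive artery.
- **Intra-operative observations.** The artery is harvested when two criteria are met. Criterion A, scored on the Radial Artery Quality Evaluation Survey, covers the artery's own characteristics and also requires that "quality of harvesting technique and surgical accessibility are considered satisfactory, good or optimal". Criterion B is a thumb SpO2 of at least 95% "when an occlusive atraumatic clamp is applied on the mobilised RA".
- **Inclusion (section 2).** Patients have elective or urgent CABG with radial artery harvesting, and the artery has already been chosen as a conduit.
- **Statistical Analysis (section 3).** The only content is how N was obtained: "Sample size calculation was undertaken using G*Power software (version 3.1"), with a chi-squared test, effect size 0.4 and power 0.8.

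**The concern.** None of the four primary measures can be computed until something defines which arteries were truly harvestable. With nothing named, that choice would be made after the data are seen.

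The exposure rule adds a second problem. Any intra-operative reference needs an exposed artery, and criterion B needs a mobilised one. If exposure follows a negative ultrasound, the arteries that reach the reference are the test-negatives. A 2x2 table holding only test-negatives has no true positives and no false positives. It shows 100% specificity, and 0% sensitivity if any verified artery is non-harvestable, whatever the test's real accuracy. The Modified Allen and Barbeau tests are affected to the extent that their positives are also withheld from exposure, since all four measures inform that decision.

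A lesser issue is that the only harvestability rule after exposure, A plus B, mixes the artery with the operator. Harvesting technique is not something a pre-operative circulation test can predict.

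**Working it through.** **The plan's own figure.** N = 69 reproduces from the noncentral chi-squared distribution with w = 0.4 and power 0.80 if alpha is 0.05 and df = 3 (power 0.806 at 69). Neither alpha nor df is stated. At alpha 0.05, df = 1, 2 and 4 give 50, 61 and 75. N is not disputed here, and the calculation says nothing about a reference standard.

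Everything below is illustration. The documents give no prevalence, accuracy or technique-failure rate.

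**Base case (assumed).** 10% non-harvestable, sensitivity 80%, specificity 90%, N = 69.
- Non-harvestable D = 6.9; sound ND = 62.1.
- TP = 0.8 × 6.9 = 5.52; FN = 1.38; FP = 0.1 × 62.1 = 6.21; TN = 55.89.
- Test-positive = 11.73; test-negative = 57.27.

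**Verification of positives.** Rounded: 12 ultrasound-positive, none exposed; 57 negative, 1 of them non-harvestable.
- Verified table: sensitivity 0/1, specificity 56/56, PPV 0/0. NPV is 56/57 = 98.2% (exact 95% CI 90.6% to 99.96%).
- Let k of the 12 unverified arteries be non-harvestable, k = 0 to 12:
  - sensitivity = k/(k+1): 0% to 12/13 = 92.3%
  - specificity = 56/(68−k): 56/68 = 82.4% to 100%
  - PPV = k/12: 0% to 100%
- At 5% prevalence about 9 would be positive (9 unverified; 60 negative, 1 non-harvestable): sensitivity 0% to 9/10 = 90%, specificity from 59/68 = 86.8%.
- At 20% prevalence about 17 would be positive (17 unverified; 52 negative, 3 non-harvestable): sensitivity 0% to 17/20 = 85%, specificity from 49/66 = 74.2%.
- If half the positives of a test are verified (base case): apparent sensitivity 2.76/(2.76+1.38) = 66.7% instead of 80%; specificity 55.89/(55.89+3.105) = 94.7% instead of 90%.

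**If all positives are exposed.** The base case rounds to TP 6, FN 1. Sensitivity is then 6/7, exact 95% CI 42.1% to 99.6%, so it rests on very few arteries even with full verification.

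**Technique in the reference (conditional).** Let T = m × ND technique failures, where m is the share of all sound arteries, and let q be the share of those failures that are test-positive. All arteries are taken as verified.
- NPV = (55.89 − (1−q)T)/57.27
- Sensitivity = (5.52 + qT)/(6.9 + T)
- Specificity = (55.89 − (1−q)T)/(62.1 − T)
- PPV = (5.52 + qT)/11.73

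| Case | NPV | Sensitivity | Specificity | PPV |
|---|---|---|---|---|
| m = 0 | 97.6% | 80% | 90% | 47.1% |
| m = 5% (T = 3.105), q = 0.1 (independent of the test) | 53.10/57.27 = 92.7% | 5.83/10.005 = 58.3% | 53.10/58.995 = 90.0% | 5.83/11.73 = 49.7% |
| m = 5%, q = 0.5 | 54.34/57.27 = 94.9% | 7.07/10.005 = 70.7% | 54.34/58.995 = 92.1% | 7.07/11.73 = 60.3% |

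For m from 2% to 10%, independent of the test, NPV runs from 95.6% to 87.8% and sensitivity from 69% to 47%.

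**The case against.** **Eligibility cuts against the illustration.** Enrolled patients are to have radial harvesting with the artery already selected. Read literally, twelve unexposed ultrasound-positives among 69 is hard to square with that population. Positives might be exposed anyway, or be nearly absent through pre-selection. This stands as an alternative, but it does not settle the matter: the protocol states an exposure rule tied to a negative ultrasound and never says what happens otherwise. If pre-selection removes positives, sensitivity rests on a handful of arteries from a selected population, which is a different limitation of the same primary outcome.

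**The protocol never says that ultrasound-positive arteries go unexposed.** A reader might infer it from the rule, but the text gives only the condition for exposure. The conclusion has to stay conditional.

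**The technique effect needs three unstated conditions:** that A plus B is the reference, that a poor technique rating alone fails A, and that such ratings occur. A plus B is written as a rule for harvesting, not as a reference standard. The survey is a secondary outcome, and its form and scoring are not in the documents. Using B alone, or the artery items alone, fits the text equally well and removes the effect. This objection stands, so technique is a secondary point. Nor does NPV always shrink by the factor (1−m): that holds only when failure is independent of the test. At q = 0.5 the share among sound test-negatives is 1.55/55.89 = 2.8%, not 5%. Specificity and PPV do not fall in either case shown.

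**Conclusion.** The concern holds on two textual points that need no assumption: the primary accuracy measures have no reference standard, and nothing secures verification of test-positive arteries while exposure is tied to a negative ultrasound. This is more than missing detail, because following the stated rule can leave ultrasound sensitivity, specificity and PPV as artefacts of who was exposed, with only NPV estimable. The bounds shown (sensitivity 0% to 92.3%, specificity 82.4% to 100%, PPV 0% to 100%) rest on assumed counts and on no positives being exposed.

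Two stronger readings are not supported: that the trial will certainly leave all positives unverified, and that operator technique will depress NPV. The first is not stated and sits awkwardly with the inclusion criteria; the second depends on the conditions above, and m may be zero. The sponsor should resolve the point before analysis; confidence is medium.

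**What to change.** State in the protocol whether test-positive arteries are expected to be exposed, unexposed or largely absent through pre-selection, so that the exposure rule and the inclusion criteria are reconciled. Then, for the accuracy analysis only:

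1. Pre-specify one primary reference standard from data already collected: the survey's artery items (diameter, calcifications, pulsatile flow) plus the clamp SpO2 criterion, at the thresholds already given under Intra-operative observations. Keep harvesting technique out of the 2x2 tables and report it descriptively, after confirming that the survey records it as a separate item. Put surgical accessibility in a sensitivity analysis.
2. Report the artery items alone and SpO2 alone as secondary references. Disclose that the first overlaps with ultrasound (diameter, calcifications) and the second with Barbeau (thumb oximetry with the radial artery occluded), which could raise apparent accuracy.
3. For each test, report how many test-positive and test-negative arteries were verified, with exact intervals. Show arteries without a complete reference in best-case and worst-case bounds.
4. For any test with no verified positives, report NPV only and omit sensitivity, specificity and PPV.

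Clinical decisions to expose or harvest are unchanged. The cost is analysis wording, a few more tables, a reference that overlaps with index tests, and fewer reportable accuracy figures. The fix does not supply missing verification; it stops unsupported figures being reported.

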- **Post-operative observations.** Patients' finger movements, cold tolerance sensitivity and tactile/touch perception is measured through an ordinal symptoms scale (Follow-up Radial Artery Harvesting Scale) at post-operative day 2-5 and at follow-up appointment (3-6 weeks after surgery). Bilateral comparison between hands and forearms will be undertaken. Tactile perception is assessed through Semmes-Weinstein monofilaments (single touch). Cold sensitivity is assessed through the use of ice-pack.

The Follow-up Radial Artery Harvesting Scale was developed from a verbal rating scale (VRS) questionnaire documented in the literature and considered an accurate rating method for pinpointing the intensity of cold sensation. The VRS questionnaire was re-adapted to appreciate people's post-operative experience with their finger movements, cold sensitivity and tactile/touch perception of their forearm and will be used in this cross-sectional study. A Patient and Public Involvement and Engagement (PPIE) was undertaken on the Follow-up Radial Artery Harvesting Scale, gaining feedback from 9 adult cardiac patients from a clinical institution from the Greater London region. The PPIE resulted in improving readability and clarity of the questions and answers included in the scale.

2. Patient Recruitment Criteria

Study Population

- Sixty-nine patients from two cardio-thoracic clinical institutions from the East of England and Greater London regions.
- Cardiovascular sample group.
- Recruitment period: April 2024 – February 2025.
- End of study: 31st March 2025.
The end of study is the date of the completion of any follow-up monitoring and data collection described in the protocol.

Inclusion

- Diagnosis of ischaemic heart disease / coronary artery disease
- Age \geq 18 years
- Male and Female participants
- Elective or urgent coronary artery bypass graft (CABG) surgery and radial artery (RA) harvesting, with the RA being selected as one of the autologous graft conduits for the coronary revascularisation.

Exclusion

- Paediatric patients
- Emergency CABG
- Patients lacking capacity to consent
- Patients with limited understanding of English language and non-English-speaking patients requiring use of interpreters

Recruitment

- The planned recruitment target rate is:
 - April – August 2024: 34 patients
 - September 2024 – February 2025: 35 patients
- The recruitment rate has been calculated based on evidence from retrospective data.

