Intra-operative oxygen saturation reading	

Informed Consent Procedure

- Patients will receive written and verbal information about the trial.
- Written informed consent will be obtained by a member of the trial team after a suitable time has elapsed during which the patient has had time to read the information sheet, consider the trial and ask any questions (Consent form). The Investigator must explain to each patient the nature

of the study, its purpose, the procedures involved, the expected duration, the potential risks and benefits involved and any discomfort it may entail (Ref. *International Conference of Harmonisation of Good Clinical Practice (ICH/GCP)5 4.8.7*

- The ultimate responsibility for obtaining written informed consent lies with the Investigator but this responsibility may be delegated to a suitably trained, and experienced person.
- Prior to the patient's participation in the study, the written informed consent form must be signed and personally dated by the patient and by the clinician who conducted the informed consent discussion (Ref. *ICH/GCP 4.8.8*). Each box at the end of each statement on the consent form must be signed by the patient.
- Each subject must be informed that participation in the study is voluntary and that he/she may withdraw from the study at any time and that withdrawal of consent will not affect his/her subsequent medical treatment (Ref. *ICH/GCP 4.8.10*).
- A copy of the informed consent document will be given to the patient (Ref. *ICH/GCP 4.8.11*). One copy will be filed in the patient's hospital case notes and a copy filed in the Trial Management File by the Clinical Research Nurses.
- The Clinical Research Nurse will ensure that the patient does not have any trial specific procedures prior to giving informed consent.
- If a patient withdraws their consent a line will be drawn diagonally through the consent form and labelled 'consent withdrawn' and signed and dated by a member of staff (please refer to Section 8 re labelling of case notes).

5. Follow-up Visits and Travel Expenses

Follow up Visits

The follow up visits will be in accordance with the visit schedule in table 1. The patients will be seen by the Researcher or Clinicians directly involved in the primary care for the patients for conducting the above presented observations. Clinicians directly involved in the patient care include Surgical Care Practitioners, Cardiothoracic Specialist Registrars and Advanced Nurse/Clinical Practitioners.

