Travel Expenses

Participants are not required to travel to take part in the study as data will be collected during their hospital stay and during their pre- and/or post-operative follow up appointments to the clinical institutions.

6. Data Collection

Data Collection Form Completion

- The Investigator will ensure the accuracy, completeness, legibility and timeliness of the data recorded in the data collection forms (DCFs) and in all required reports to the Sponsor, R&D and REC.

Source Documentation

- The investigator must maintain source documents (patient's hospital case notes) for each patient in the study, consisting of all demographic and medical information, including laboratory data, and radiology results. A copy of the consent form and patient information sheet will also be filed in the patient's case notes. All information in the DCFs, apart from the questionnaires, must be traceable to and consistent with the source documents in the patient's hospital case notes (Ref. ICH/GCP 4.9.2).

Errors and Corrections

- Any change or correction to the DCF will be dated, initialled, and explained (if necessary) and should not obscure the original entry.

Storage of Documents

- DCFs will be kept in a locked filing cabinet or a locked room.

Retention of Documents

- All study documentation will be stored for 15 years after the last patient has completed their last visit.

Monitoring and Audit

- Upon request of the monitor, auditor, Sponsor, R&D, REC, MHRA or other regulatory authority, the Investigator will make available for direct access all requested study-related records.

The project data will be monitored by the Research Officer monthly. The first two patients from each participant site will be monitored in full. Thereafter fifty percent of the data will be monitored every month during the recruitment phase. After recruitment is complete ten percent of the data will be monitored.

7. Adverse and Serious Adverse Events

The definition of an adverse event is: 'Any untoward medical occurrence in a patient which does not necessarily have a causal relationship with this treatment'. This includes 'any unfavourable and unintended sign (including an abnormal laboratory finding), symptom or disease temporally associated with the study drug'. This may include, for example, a cold or an accident.

The definition of a serious adverse event is one that fulfils at least one of the following criteria:

- Is fatal- results in death
- Is life threatening

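### Table 1 leaves out the post-operative day 2-5 assessment and states no time origin, and the 31 March 2025 end of study falls before the last permitted follow-up visits

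*Combined protocol and SAP*

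**What the plan says.** **Number and timing of assessments.** Section 1, Schedule of Events (Post-operative observations), has the scale measured "at post-operative day 2-5 and at follow-up appointment (3-6 weeks after surgery". That is two assessments, both counted from surgery.

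Table 1 in Section 4 has a row "Post-operative observation (Follow-up Radial Artery Harvesting Scale") with a single mark, under visit n+2, whose interval is week 4-12. There is no mark under visit n+1, which holds the pre- and intra-operative measures at week 0-3, and no column for day 2-5. The consent visit also has the interval week 0-3. No origin for the weeks is given.

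**Status of Table 1.** Section 4 (Follow-Up Visits): "Visits should be scheduled and performed according to table 1". Section 5 (Follow up Visits): "The follow up visits will be in accordance with the visit schedule in table 1". Section 5 also says that patients are seen "for conducting the above presented observations", and its Travel Expenses paragraph says that "data will be collected during their hospital stay" as well as at appointments.

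**Dates.** Section 2 (Study Population): "Recruitment period: April 2024 – February 2025". The same list gives 31 March 2025 as the end of study and defines the end of study as the date on which all follow-up and data collection are complete. Section 2 (Recruitment) plans "September 2024 – February 2025: 35 patients". Section 1 (Study Design) puts the longest expected participation at 12 weeks.

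**The concern.** There are two inconsistencies.

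1. The narrative and the governing table disagree on how many times a secondary outcome is measured. A site working from Table 1 alone would not be scheduled to collect the in-hospital assessment. The late windows are also written differently, and with no origin in Table 1 they cannot be compared without an assumption.
2. The stated end date leaves 31 days after the last permitted recruitment day. That is shorter than the 6-week limit in Section 1 and the 12-week limit in Table 1. The date therefore disagrees with the definition printed beside it. If it is enforced, the late assessment is cut short, or in a few cases lost, for the last recruits.

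The protocol gives no analysis of this scale by time point, so no effect on an analysis is claimed. What is at stake is the completeness of a secondary outcome.

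**Working it through.** **Inputs.** Section 1: day 2-5 and 3-6 weeks after surgery; 12-week maximum participation. Table 1: consent and surgery visits at week 0-3, scale at week 4-12. Section 2: recruitment to February 2025; 35 patients from September 2024 to February 2025; end of study 31 March 2025; N = 69.

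**Assumptions.** Week 3 is day 21 and week 4 is day 28. Surgery is at visit n+1, at week s = 0 to 3. Consent is at week c = 0 to 3. The last recruit is on 28 February 2025. Recruitment is uniform.

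**Step 1: can the single Table 1 entry hold both assessments?** Day 2-5 after surgery falls on study days 7s+2 to 7s+5. The Section 1 late window falls in study weeks s+3 to s+6. Table 1 allows a visit 4-s to 12-s weeks after surgery.

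| Surgery week s | Day 2-5, study days | Section 1 late window, study weeks | Share inside week 4-12 | Table 1 window, weeks after surgery |
|---|---|---|---|---|
| 0 | 2-5 | 3-6 | 2/3 | 4-12 |
| 1 | 9-12 | 4-7 | all | 3-11 |
| 2 | 16-19 | 5-8 | all | 2-10 |
| 3 | 23-26 | 6-9 | all | 1-9 |

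Every early assessment falls before day 28, when week 4 opens. If week 3 is read as running to day 27, surgery on days 23-27 puts post-operative day 5 on days 28-32, but one entry still cannot hold two assessments. The late windows largely overlap, and Table 1 is the wider.

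One of two assessments per patient is missing from the table. If all 69 patients have both (138 in total), 0 are at risk if sites follow Section 1 and 69 if all follow Table 1 alone. This is a bound, not an estimate.

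**Step 2: is 31 March 2025 reproduced?** From 28 February to 31 March is 31 days. The latest visit after consent is s + 6 = 6 to 9 weeks under Section 1 and 12 - c = 9 to 12 weeks under Table 1.

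| Rule | Days after consent | Last visit | Days after 31 March |
|---|---|---|---|
| Section 1, surgery same day | 42 | 11 April | 11 |
| Section 1, surgery 3 weeks later | 63 | 2 May | 32 |
| Table 1, consent at week 3 | 63 | 2 May | 32 |
| Table 1, consent at week 0 | 84 | 23 May | 53 |

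No row gives 31 March. To keep that date with full windows, the last consent would have to be 17 February (6 weeks), 27 January (9 weeks) or 6 January (12 weeks). If the last recruit is instead on 1 February, the last visits are 15 March to 5 April under Section 1 (0-5 days late) and 5 to 26 April under Table 1 (5-26 days late).

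**Step 3: how many patients?** 1 September 2024 to 28 February 2025 is 181 days, so the rate is 35/181 = 0.193 per day.

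- *Late window shortened:* 11 x 0.193 = 2.1, 32 x 0.193 = 6.2, 53 x 0.193 = 10.2. That is about 2-6 patients under Section 1 and 6-10 under Table 1.
- *Not assessable at all by 31 March, Section 1:* for a 28 February recruit the window opens on 21 March, 28 March, 4 April or 11 April for surgery 0, 1, 2 or 3 weeks after consent. That gives 0, 0, 4 x 0.193 = 0.8 and 11 x 0.193 = 2.1 patients.
- *Not assessable at all by 31 March, Table 1:* the window opens 4 - c weeks after consent, on 7 to 28 March, so 0 patients.

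**The case against.** - **The protocol read as a whole still covers the early assessment.** Section 5 refers back to the observations already described and to data collected in hospital, so a careful site would do it. This stands in part: the assessment is unscheduled, not excluded. But Table 1 lists other in-hospital measures, so it is not a list of outpatient visits only, and two sections name it as the schedule.
- **The end date may be only a projection.** The definition beside it is event-based. If the definition governs, no data need be lost. The date is then still inconsistent with the definition. With same-day surgery and the Section 1 window, patients consented up to 17 February also finish in time; the overrun concerns those recruited later, which Section 2 permits.
- **The figures depend on conventions that the protocol does not state.** If Table 1 counts from surgery, with surgery three weeks after consent, week 4 opens 21 + 28 = 49 days after a 28 February consent, on 18 April. About 18 x 0.193 = 3.5 patients would then be unassessable under Table 1, not 0. That reading fits poorly with a surgery column of week 0-3, and it would take follow-up to 3 + 12 = 15 weeks after consent, beyond the 12-week maximum. The 0 is therefore conditional on an origin at or before consent. If week 3 runs to day 27 and week 12 to day 90, the upper overruns become 38 days (8 May) and 59 days (29 May), which makes the problem larger.
- **The bound of 69 assumes that every patient gets the scale.** Section 1 makes harvest conditional on pre- and intra-operative findings and does not say whether unharvested patients are assessed. Section 3 also lets the sample size be updated. Both points stand, so 69 is a ceiling at the planned size.

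**Conclusion.** The concern holds and is minor. Table 1 schedules one of the two assessments that Section 1 requires. The stated end of study is 11-53 days before the last permitted visit for a patient recruited on 28 February 2025. About 2-10 of 69 patients would have a shortened late window, and about 0-2 would have none before the stated date.

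The dates rest on recruitment to the last day of February, surgery 0-3 weeks after consent, and Table 1 weeks counted from a point at or before consent. The patient counts also assume uniform recruitment at the planned rate. The two late windows are not in outright conflict: between two-thirds and all of the Section 1 window lies inside Table 1's. The missing time origin alone would be only a gap in detail. Only a secondary outcome is affected.

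**What to change.** Reconcile the post-operative paragraph of Section 1 with Table 1 so that both give the same number of assessments and the same windows, and state in Table 1 what the weeks are counted from. Which schedule is right is for the sponsor to decide. Then set the end-of-study date to the last recruitment date plus the longest reconciled interval to the final visit, or close recruitment earlier by the same amount.

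The cost is a short amendment to one table, one paragraph and one date. On the figures above, the study closes 11-53 days (about 2-8 weeks) later. Alternatively, recruitment stops that much earlier, which at the planned rate forgoes about 2-10 of the 69 patients unless the rate rises.
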